We will recruit up to 30 veterans with prediabetes to participate in the LC-DPP. The intervention will be delivered in partnership with VA Certified Diabetes Educators who will serve as lifestyle coaches for the group-based intervention. The LC-DPP lifestyle coaches will deliver 16-weekly one-hour group sessions over the first 6 months and 8 maintenance sessions over the subsequent 6 months. **Table 1** shows session topics. Participants will receive a binder to hold study materials. They will be provided with printed handouts on a session-by-session basis. Individuals that are absent for a particular session will receive corresponding session materials by e-mail or postal mail.

The CDC's Diabetes Prevention Program instructs participants to adhere to a fat-restricted diet with an explicit cap of less than 33-55 grams of fat per day depending on starting body weight. In contrast, LC-DPP participants will be initially instructed to follow *ad-libitum* very low-carbohydrate diet, which restricts carbohydrate intake (not including fiber) to 20-35 grams per day with the goal of achieving nutritional ketosis. Participants will be encouraged to eat a normal amount of protein (roughly 80-120 grams per day) and to derive the remaining calories from fat. Allowable foods include: meats, fish, poultry, eggs, cheese, seeds, nuts, leafy greens, non-starchy vegetables, and some fruits.

During the LC-DPP's maintenance phase, participants will be instructed to gradually reintroduce carbohydrates (e.g., 5 non-fiber grams of carbohydrates per week) if: (1) they have met their weight loss target and (2) if they desire to liberalize their carbohydrate intake.

To minimize potential side effects (e.g. headache, constipation, muscle cramps, diarrhea, general weakness, and rash) participants will be instructed to replace one meal a week with a low-carbohydrate alternative, starting with breakfast. Participants will be counseled to drink sufficient water and to consume adequate sodium. Further, primary care providers will be notified of their patients' involvement in this study, and they will be given a handout that describes the intervention, potential side effects, and strategies to minimize side effects.

Session Number	Topic
Core phase	
0	Study information session (Informed consent to be obtained)
1	Welcome to the Low-Carb Diabetes Prevention Program
2	Be a Carbohydrate Detective
3	Low-Carb Meals
4	Low-Carb Cooking and Shopping
5	Move Those Muscles

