Change in body weight: Body weight will be measured and recorded at each attended session. We will calculate average body weight change and percent body weight loss at the end of the program's core phase (6 months) and maintenance phase (12 months). Among session non-attendees, we will attempt to schedule 6- and 12-month weigh-ins at participants' convenience within 2 weeks of the final core and maintenance sessions. All weights will be obtained using the same calibrated scale.

Change in HbA1c: We will calculate change in HbA1c from baseline to 6 and 12 months

Change in lipids: We will calculate change in triglycerides and total cholesterol/HDL ratio from baseline to 6 months and 12 months.

Change in survey measures: We will calculate change in self-reported survey measures from baseline to 6 months and 12 months.

Fidelity: We will measure intervention fidelity (i.e., extent to which components of an intervention are delivered as intended) using quantitative measures adapted from the literature²⁶ as well as qualitative interview feedback from participants and dietitians.

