Low-Carbohydrate Diabetes
Prevention Program Among
Veterans With Prediabetes (VA LC-
DPP)

Prepared for ClinicalTrials
Resubmission 4/20/21

Statistical Analysis Plan:

Quantitative analysis

Descriptive statistics will be used for baseline survey response data including demographic and socioeconomic characteristics. For all continuous outcomes, we will calculate mean change and standard deviation from baseline to 6 months and 12 months and compare outcomes from baseline to 6 months and 12 months using paired t-tests. For all categorical outcomes, we will use chi-square or Fisher's exact tests to examine changes from baseline to 6 and 12 months. All analyses will be conducted using Stata 14.

Qualitative analysis:

Semi-structured interviews will be recorded and transcribed verbatim. Interviews will then be imported into qualitative analysis software. Two investigators will independently read and code transcribed interviews. Interviews will then be coded jointly using consensus conferences. Interviews will be analyzed using directed content analysis²⁷, which is to say that codes will be created to reflect the main topics in the interview guide and to characterize the patterns and themes that emerged from the data.²⁸

**Cravings:
Control of Eating Questionnaire**

Over the past 7 days...

How strong was your desire to eat sweet foods?	Q1	Answer choices on a sliding scale from 0 to 100 with anchors at 0 and 100:	Items on the CoEQ are assessed by 100 mm VAS with items relating to each subscale being averaged to create	Dalton M, Finlayson G, Hill A, Blundell J. Preliminary validation and principal components analysis of the Control of
How strong was your desire for non-	Q2	0- not at all strong 10 20	to create	

Over the past 7 days, how often have you had cravings for

Sweet foods like	Q3	Answer choices	
Other sweet foods (cakes, pastries, cookies, etc)?	Q4	on a sliding scale from 0 to 100 with anchors at 0 and 100:	
Fruit or fruit juice?	Q5	0- not at all	
Dairy foods (cheese, yogurts, milk, etc)?	Q6	10 20 30 40 50 60 70 80 90 100-	
Starchy Foods that are not sweet like French fries, potato chips,	Q7 Q8	70 80 90 100- extremely often	

Stress Eating

Please indicate how you usually experience a stressful event

I eat more of my favorite foods to	Q1	Answer choices 1 through 4 with anchors on 1 and 4:	Reverse code and sum, so that higher scores indicated	Tsenkova, V., Boylan, J. M., & Ryff, C. (2013). Stress
------------------------------------	----	---	---	--

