5
6
7- you must include them, they were very helpful

Do you have any suggestions about how we can improve the handouts? Which were your favorite or least favorite topics?

Q7

Participants may enter free text of whatever they choose.

Social Support

How often in the last 30 days has your family or friends

Encourage	Q1	1 =	Average	Norman,
Discuss	Q2	Almost	responses	G. J.,
Remind	Q3	never	of the 6	Carlson, J.
you to		2 = Once	questions.	A., Sallis,
choose		in a while	**NOTE:	J. F.,
healthy		3 =	this just	Wagner,
foods.		Sometime	appears	N., Calfas,
Share	Q4	s	to be how	K. J., &
ideas on		4 = Often	it is in the	Patrick, K.
healthy		5 =	scoring,	(2010).
eating.		Almost	but	Reliability
Eat	Q5	always	doesn't	and
healthy			actually	validity of
meals			say how	brief
with you.			to do it.	psychosoc
Complain	Q6			ial
about				measures
eating				related to
healthy				dietary
foods.				behaviors.

Open Ended Support

Have you gotten any feedback from family, friends, or physicians /healthcare providers about this program or your experience with it? If so, what did they say?
	
Q1
	
Participants may enter free text of whatever they choose.
	
NA
	
NA

--	-----------	---	-----------	-----------

Medication Changes

6- month question

Did any of your medications or doses change since starting this program?
	
Q1
	
Yes/No

If yes, please specify which medications were changed or added.
		
Free text

If yes,	Q2	Increased
was the		Decrease
dose		d
increased		I don't
or		know
decreased		
?		

12-month question

Did any of your medications or doses change over the past 6 months program (i.e. maintenance phase)?	Q1	Yes/No
If yes, please specify which medications were changed or added.		Free text
If yes,	Q2	Increased
was the		Decrease
dose		d
increased		I don't
or		know
decreased		
?		

Diet Evaluation

How much do	Q1	Answer choices 1-	NA	NA
-------------	----	-------------------	----	----

How much do you think this diet has improved your physical health? Q2 7 with anchors 1,7: 1- Not at all 2 3 4 5

How much do you think this diet has Q3 6 7- Very much so

How hard is it to stay on your diet? Q4 Answer choices 1-7 with anchors 1,7: 1- Very easy 2

How often do you cheat on your diet? Q5 Answer choices 1-7 with anchors 1,7: 1- Not at all 2 3 4 5 6 7- Very often

Open Ended Diet

When you Q1
follow
this low-
carbohydr
ate food
plan:
What
about
your
health got
better?

Participa NA NA
nts may
enter free
text of

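### The SAP's social support key averages six items without reversing the one about complaining, so, scored literally, more complaining counts as more support

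*SAP*

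**What the plan says.** The Social Support block of the SAP opens with the stem "How often in the last 30 days has your family or friends" and lists six behaviours on a single five-point frequency scale, from 1 (almost never) to 5 (almost always). Reminding, sharing ideas and eating healthy meals together (Q3 to Q5) are legible. Only the first words of Q1 (encourage) and Q2 (discuss) survive. Q6 is complaining about healthy food. The scoring cell says to average the six responses. A note beside it says that this seems to be the scoring but that the source does not say how to do it. There is no reversal, no separate subscale and no statement of direction.

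Elsewhere the same SAP does deal with item direction. The Stress Eating block says "Reverse code and sum, so that higher scores indicated" (the rest of that cell is cut off). The PROMIS pain item has a written recode. The self-regulation questionnaire sends items of different meaning to three separate scores.

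On use of the score, Protocol section 5.5 says, under secondary measures, "We will calculate change in self-reported survey measures from baseline to 6 months and 12 months". For continuous outcomes the SAP will "compare outcomes from baseline to 6 months and 12 months using paired t-tests". On size, Protocol section 5.1 says "We will recruit up to 30 veterans with prediabetes to participate in the LC-DPP".

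**The concern.** A plain average treats all six behaviours as pointing the same way. Five read as support and one as discouragement, so a high answer to Q6 pushes the score up when it should pull it down. Two things are at stake. A real change in support can be scored as smaller than it was, or in some patterns with the wrong sign. And with the rule unsettled, whether to reverse Q6 becomes a choice that could be made after the data are seen. The pilot is meant to inform a larger comparative trial, so an unclear key could also be carried forward.

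**Working it through.** The documents give no range, power or expected change for this scale, so there is no figure of the plan's own to reproduce.

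**Inputs.** Six items scored 1–5 and a plain mean (SAP, Social Support); the key is silent on reversing Q6 (same place); up to 30 participants (Protocol 5.1).

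**Two scores.** As written: A = (Q1+…+Q5+Q6)/6. With Q6 reversed: B = (Q1+…+Q5+(6−Q6))/6. Hence A − B = (2·Q6 − 6)/6 = (Q6 − 3)/3.

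**Levels.**
- Most supportive pattern (5,5,5,5,5,1): A = 26/6 = 4.33; B = 30/6 = 5.00.
- Least supportive pattern (1,1,1,1,1,5): A = 10/6 = 1.67; B = 6/6 = 1.00.
- Distance between these two patterns: A gives 2.67, B gives 4.00, so A is one third narrower.
- A household that always does all six, complaining included: A = 30/6 = 5.00; B = 26/6 = 4.33. The formal range of A is therefore still 1 to 5. The narrowing applies only where Q6 runs opposite to the rest.

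**Changes.** Let S be the summed change on Q1–Q5 and c the change on Q6. Then ΔA = (S + c)/6 and ΔB = (S − c)/6.
- Every item improves by d (S = 5d, c = −d): ΔA = 4d/6 = 0.67d; ΔB = d.
- Only complaining falls, by one point (S = 0, c = −1): ΔA = −0.17; ΔB = +0.17.
- Q6 unchanged (c = 0): ΔA = ΔB = S/6, so no change is lost.
- Support rises (S > 0) and complaining falls by f (c = −f): ΔA is negative only if f > S, that is, only if the fall in Q6 is more than five times the mean gain on Q1–Q5.

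**Effect on the paired t-test (illustration only).** A smaller raw change is not an equal loss of sensitivity, because the standard deviation changes too. Assume equal improvement and unit variance on all six items, and a common correlation ρ between change scores once direction is aligned. The variance of the item sum is then 6 + 30ρ reversed and 6 + 10ρ unreversed. The ratio of standardised changes is [4/√(6+10ρ)] / [6/√(6+30ρ)]. Assume further a standardised change of 0.5 on the reversed score, n = 30 and two-sided 0.05. None of these values is in the documents. Power with Q6 reversed is 0.754.

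| ρ | ratio | power, unreversed |
|---|---|---|
| 0 | 0.667 | 0.423 |
| 0.3 | 0.861 | 0.625 |
| 0.5 | 0.921 | 0.684 |
| 0.7 | 0.961 | 0.720 |

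**The case against.** The strongest reply is that the plan does not forbid reversal. Its note shows that the team saw the scoring was unclear, the instrument is cited as validated, and the developers' scoring cannot be checked from these documents. They may reverse Q6, score it apart, or do neither. Imposing 6 minus Q6 without looking could break comparability with the published scale. This stands, and it shapes the fix. It does not clear the key: the one instruction on the page is to average all six, and an analyst who follows it adds complaining to support.

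It is also fair that Q1 and Q2 are truncated, so calling them supportive is an inference, though a natural one.

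A reader might infer that the score's range is cut by a third for everyone, or that the reported change in support will come out with the wrong sign. The documents support neither. The formal range stays 1 to 5, the two scores change identically when Q6 does not move, and an improvement is reversed only under the condition shown above. The loss of test sensitivity is large only if the items are nearly uncorrelated, which would be unusual within one scale.

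Finally, social support is not among the survey domains named in Protocol section 5.5. It enters through the instrument list in section 6.41 of the application and the general line on survey change. Because the score is built from item responses, Q6 can be rescored at analysis.

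**Conclusion.** The point holds, as a minor one. The key as written gives a support score that rises with complaining, and its own note leaves the matter unresolved. The size depends on how Q6 moves relative to Q1–Q5: no loss of change if Q6 is static, one third of the raw change if all six items improve equally, and the wrong direction if only Q6 changes. In the illustration, power falls from 0.75 to between 0.42 and 0.72 depending on ρ. That range rests on assumed values.

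Two further inferences should be resisted. Silence on reversal does not show that the analysis will omit it. Nor does the point reach the study's main conclusions: feasibility and acceptability are the primary outcomes and do not use this score, and no decision rule depends on it. The conclusion assumes that Q1 and Q2 are supportive items.

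**What to change.** Before analysis, check the cited instrument's scoring and amend the SAP's Social Support key to whichever of these matches it:

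- recode Q6 as 6 minus the response, then average all six items; or
- average Q1–Q5 as support and report Q6 separately as discouragement.

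State that higher means more support, and replace the note with the rule adopted. If the source does not settle the matter, choose one of the two before the follow-up scores are examined and record the reason.

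The cost is one line in the scoring key. No new data, visits or questionnaire changes are needed.
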